HPV Vaccine Intervention for Young Sexual Minority Men

NCT04032106

March 8, 2021

STUDY AIMS

This study will evaluate a mobile health (mHealth) HPV vaccine intervention (called the *Outsmart HPV* intervention) for young sexual minority men (YSMM). In doing so, we will conduct a randomized controlled trial (RCT) of unvaccinated YSMM ages 18-25 from the US recruited via social media. We will randomize YSMM to: a) standard information about HPV and HPV vaccine via a mobile-friendly website (control group); b) *Outsmart HPV* with unidirectional vaccine reminders (Out-U group); or c) *Outsmart HPV* with interactive vaccine reminders (Out-I group). Specific aims are to:

Aim 1: Determine the efficacy of the *Outsmart HPV* intervention on increasing HPV vaccine initiation and completion. Hypothesis 1a: HPV vaccine initiation (i.e., receipt of at least one dose of the three-dose HPV vaccine series) and completion (i.e., receipt of all three doses) will be higher among participants in both the Out-U and Out-I groups compared to the control group. Hypothesis 1b: HPV vaccine initiation and completion will be higher among participants in the Out-I group compared to the Out-U group.

Aim 2: Identify mediators that explain the relationship between study arm and HPV vaccine initiation and completion. Hypothesis 2: The effects of the intervention will be mediated by changes in theoretical constructs, including increased perceived vulnerability to HPV and HPV-related disease, reduced response costs of getting HPV vaccine (e.g., reduced concerns about vaccine safety and side effects), increased self-efficacy to get HPV vaccine, and increased intention to get HPV vaccine.

Aim 3: Determine if intervention efficacy differs across key demographic and health-related characteristics of participants. Hypothesis 3: Intervention effects will be stronger (i.e., moderation) among participants who are not married or in a relationship, live in urban areas, report having a routine medical check-up in the last year, or report having disclosed their sexual orientation to a healthcare provider.

FUNDING

This study is funded by the National Cancer Institute (NCI) Grant #R37CA226682 (originally awarded as Grant #R01CA226682). Please note the mHealth intervention was developed and pilot tested in a previous NCI-funded study (R21CA194831), and the current study extends this line of research.

BACKGROUND

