2.m. Sample Size/Data Analyses. We will randomize about 2100 men (700 per arm), expecting 70% retention over the 9-month follow-up (based on our pilot study). We are confident in reaching this sample size given the large number of YSMM on social media and that similar sample sizes have been recruited via social media.^{64,65} All analyses will use an intent-to-treat approach.

Aim 1 (Efficacy). We hypothesize HPV vaccine initiation and completion will be higher among participants in both the Out-U and Out-I groups compared to participants in the control group (Hypothesis 1a). Further, we hypothesize that HPV vaccine initiation and completion will be higher among participants in the Out-I group compared to participants in the Out-U group (Hypothesis 1b).

We will first examine descriptive statistics (i.e., proportions and 95% confidence intervals [CIs]). We will then use logistic regression to test our hypotheses, with separate models for HPV vaccine initiation and completion. Models will control for any potential confounders (i.e., variables that differ between study arms [$p < 0.10$] at baseline). For each outcome, we will perform all pairwise comparisons of study arms, using a Bonferroni corrected two-sided alpha of 0.017 to control the overall type I error rate. We will have at least 80% power for all comparisons,⁶⁶ assuming our

projections of initiation (control=20%; Out-U=35%; Out-I=45%) and completion (control=10%; Out-U=22%; Out-I=35%). Projections are based on pilot study results and past work on different types of reminders.^{67,68} Logistic regression models will produce odds ratios (ORs) and 95% CIs. Results will determine the efficacy of *Outsmart HPV* and identify which type of HPV vaccine reminder most effectively increases vaccination.

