Aim 3 (Moderation). We will examine demographic and health-related characteristics from the screener and T1 surveys as potential moderators. We hypothesize intervention effects will be stronger (i.e., moderation) among YSMM who are not married or in a relationship (due to higher perceived vulnerability to HPV and HPV-related disease), live in urban areas (due to greater access to care, including LGBT-friendly providers), report having a routine medical check-up in the last year (due to higher utilization of healthcare and self-efficacy to get HPV vaccine), or report having disclosed their sexual orientation to a healthcare provider (due to higher self-efficacy to talk with a healthcare provider about HPV vaccine) (Hypothesis 3). We expect moderators will be similar for both HPV vaccine initiation and completion (which will be examined as separate outcomes).

We will use logistic regression models that include an interaction term between each potential moderator and study arm to test this hypothesis and identify moderators. Logistic regression models will produce ORs and 95% CIs. We will consider an interaction present if an interaction term has $p<0.05$. Given our analytic sample size, we will have 80% power to detect interaction terms with ORs>2.30. Results will determine if intervention efficacy differs by demographic and health-related characteristics.

2.n. Potential Challenges. Recruitment: We have expertise recruiting YSMM via social media^{26,44,73-77} and will offer study incentives. **Retention:** We expect 70% retention based on our pilot study and will provide incentives and survey notifications to aid retention. **Missing data:** Missing survey data will be minimized by using prompts for skipped items. This resulted in less than 5% missing data in our pilot study. **Outcome ascertainment:** HPV vaccination status will be confirmed by medical records if MRR is provided, otherwise self-reported data will be used. **Generalizability:** To maximize

generalizability, participants will be recruited throughout the US. YSMM recruited via Facebook in our pilot study were demographically similar to YSMM from nationally representative samples.²⁶⁻²⁸ **Contamination:** We do not expect contamination since we will recruit throughout the US, the project website will require login, and participants will receive only the study materials for their randomized study arm.

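### The stated 80% power for interaction ORs above 2.30 fits initiation against control, but for completion against control the plan's own projections give only about 60% (Out-U) and 64% (Out-I)

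*Combined protocol and SAP*

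**What the plan says.** The power statement for moderation is one sentence in section 2.m, Aim 3: "Given our analytic sample size, we will have 80% power to detect interaction terms with ORs>2.30". The analysis is described as "logistic regression models that include an interaction term between each potential moderator and study arm", and the decision rule is "We will consider an interaction present if an interaction term has" p<0.05. Nothing says which of the three arm contrasts the term refers to, how common the moderator is, or which outcome the figure was computed for.

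The same paragraph makes clear that two outcomes are involved: "We expect moderators will be similar for both HPV vaccine initiation and completion (which will be examined as separate outcomes". Hypothesis 3 in the Study Aims is directional: "Intervention effects will be stronger (i.e., moderation) among participants who are not married or in a relationship, live in urban areas", with two further healthcare-related moderators.

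The inputs for a check are earlier in section 2.m. On size: "We will randomize about 2100 men (700 per arm), expecting 70% retention over the 9-month follow-up". On event rates, Aim 1 uses "projections of initiation (control=20%; Out-U=35%; Out-I=45%) and completion (control=10%; Out-U=22%; Out-I=35"%).

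**The concern.** A single power figure is offered for two outcomes whose projected rates differ considerably. The variance of a log interaction OR depends on the number of events in each arm-by-moderator cell. With completion projected at 10% in the control arm, against 20% for initiation, the same interaction OR cannot carry the same power in contrasts with control.

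This affects interpretation. The plan expects the same moderators for both outcomes. If power is about 80% for one and about 60% for the other, a moderator that is significant for initiation and not for completion may reflect lower power alone. A reader who applies the stated 80% to completion could take that pattern as a real difference, or read a null completion term as stronger evidence than it is.

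The plan also leaves open which contrasts the p<0.05 rule covers in a three-arm model. The power that applies depends on that choice.

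**Working it through.** **Inputs from section 2.m**
- Analysed per arm: 700 × 0.70 = 490.
- Initiation: control 20%, Out-U 35%, Out-I 45%. Completion: 10%, 22%, 35%.
- Interaction OR 2.30, so ln 2.30 = 0.833. Significance level 0.05 per term.

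**Assumptions, because the plan is silent**
- Two-sided test (Aim 3 does not state sidedness; Aim 1 is two-sided).
- Binary moderator split 50/50, so 245 per cell.
- No moderator effect in the reference arm of each contrast. In the other arm, the two rates are solved so that their average equals the projection and their OR is 2.30.

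**Formulas**
- SE² = sum over the four cells of 1/[n p(1−p)], with n the cell size.
- Power = Φ(0.833/SE − 1.96).

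**Reproducing the plan's figure: initiation, Out-U against control**
- Control 20% in both levels: 2/(245 × 0.16) = 0.0510.
- Out-U 25.7% and 44.3%: 1/(245 × 0.257 × 0.743) + 1/(245 × 0.443 × 0.557) = 0.0379.
- SE = √0.0889 = 0.298. Power = Φ(0.833/0.298 − 1.96) = 80%.

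**The same step for completion, Out-U against control**
- Control 10% in both levels: 2/(245 × 0.09) = 0.0907.
- Out-U 15.05% and 28.95%: 0.0518.
- SE = √0.1425 = 0.377. Power = Φ(0.833/0.377 − 1.96) = 60%.

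The control arm supplies 0.0907 of the total variance of 0.1425, which is where the shortfall arises.

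**All contrasts at OR 2.30, 490 per arm, even split**

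| Outcome | Contrast | SE | Power | OR for 80% power | n per arm for 80% at OR 2.30 |
|---|---|---|---|---|---|
| Initiation | Out-U vs control | 0.298 | 80% | 2.31 | 493 |
| Initiation | Out-I vs control | 0.292 | 81% | 2.27 | 474 |
| Initiation | Out-I vs Out-U | 0.265 | 88% | 2.10 | 390 |
| Completion | Out-U vs control | 0.377 | 60% | 2.91 | 790 |
| Completion | Out-I vs control | 0.359 | 64% | 2.74 | 713 |
| Completion | Out-I vs Out-U | 0.292 | 81% | 2.27 | 474 |

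Simulation with 200,000 runs per contrast agrees: 59.9% and 63.8% for completion against control.

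**Does the result depend on the assumed split?** With marginal rates held at the projections, a search over prevalence 10–90% and moderator ORs of 0.22–4.48 in the reference arm gives maximum completion power of 60% (Out-U) and 64% (Out-I) against control. Uneven moderators make matters worse for both outcomes: at an assumed 20% or 80% prevalence, initiation against control is 57–63% and completion 38–47%.

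**Does it depend on the decision rule?** Simulated at 490 per arm and an even split:

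| Rule | False positives per moderator (initiation, completion) | Power, both Outsmart arms at OR 2.30 (initiation, completion) | Completion power, one arm only at OR 2.30 | Shared OR for 80% power (initiation, completion) |
|---|---|---|---|---|
| Either control term p<0.05 | 8.7%, 8.3% | 91%, 74% | 62–66% | 2.02, 2.46 |
| Joint 2-df test | 4.9%, 4.8% | 82%, 59% | 78–82% | 2.26, 2.87 |

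**The case against.** The best counter-argument is that the sentence names no outcome or contrast, so it makes no specific claim about completion against control that could be false. Where it can be matched to the plan's inputs, for initiation, it is accurate. That is fair as far as it goes: the close match suggests, without proving, that the figure was computed for initiation. But the sentence stands unqualified in a paragraph that covers both outcomes.

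The 60% and 64% ceilings are also conditional. They require 490 analysed, a two-sided test and marginal rates equal to the projections. Relaxing these one at a time for completion against control (Out-U, Out-I) gives:
- projected rates placed in the moderator's reference level: 63% and 65%;
- one-sided test: 71% and 75%;
- all 700 per arm analysed, as an intention-to-treat reading might suggest: 75% and 79%.

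None reaches 80%. Combining 700 analysed with reference-level anchoring just reaches 80% for Out-I (78% for Out-U). However, with 700 analysed, initiation power would be 92–93%, so that reading does not explain a single figure of 80%. Pooling the two Outsmart arms at 490 per arm gives 70%.

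A further point has some force. If moderation is declared when any of the three pairwise terms has p<0.05, completion power is about 75% when both Outsmart arms share the interaction, and about 87–90% when only one arm has it, at a false-positive rate of about 12%. A joint test also reaches about 80% when one arm alone is moderated. These are statements about detecting moderation anywhere, not the power of an interaction term, and Hypothesis 3 does not single out one arm. They do show why the rule needs to be named.

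It is also true that the consequences are limited. Aim 3 does not drive the sample size, and the reported confidence intervals will show the lower precision for completion.

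**Conclusion.** The concern holds. At 490 per arm, two-sided 0.05 per term and the plan's projections, 80% power at an interaction OR of 2.30 is right for initiation against control at a roughly even split, and for Out-I against Out-U on both outcomes. It is not right for completion against control, where power is about 60% (Out-U) and 64% (Out-I) and the detectable ORs are about 2.9 and 2.7. Reaching 80% there at OR 2.30 would take about 790 or 713 analysed per arm, more than the 700 randomised.

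Moderator prevalence is an assumption, but a favourable one, so it does not create the shortfall. The unspecified contrasts are a secondary matter of missing detail; the finding rests on the power figure. This should be corrected, but it does not call the design, the sample size or Aim 1 into question.

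**What to change.** Replace the power sentence with one that states outcome, contrast and prevalence. For per-term testing, for example: with 490 analysed per arm and an evenly split moderator, power is 80% per term against control (two-sided 0.05) for interaction ORs of about 2.3 for initiation and about 2.7–2.9 for completion; uneven moderators require larger ORs.

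Add one sentence naming the arm-by-moderator contrasts to which p<0.05 applies, or stating that a joint 2-df test is used, and quote the power belonging to that choice. With a joint test and an interaction shared by both Outsmart arms, the matching ORs are about 2.3 (initiation) and 2.9 (completion). Either choice is defensible. Two control terms each at 0.05 have more power for a shared interaction but about 8–9% false positives per moderator and outcome; the joint test holds about 5% and does better when only one arm is moderated.

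The cost is a less favourable stated figure for completion and a sentence of text. Design, sample size and data collection stay as they are.

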To improve retention, the project website will send all participants email/text message notifications to complete each survey (see Appendix for Survey Notifications). For the T3 and T4 surveys, notifications will occur: 1) the day the survey becomes active; 2) 5 days after the initial invite (if the survey has not yet been completed); 3) 8 days after the initial invite (if the survey has not yet been completed); and 4) 11 days after the initial invite (if the survey has not yet been completed). For both the T3 and T4 surveys, participants will have a maximum 14-day window to complete their survey (after which the survey becomes unavailable to complete).

If a participant does not complete the T3 survey in the 14-day window, they will continue in the study and be offered the opportunity to complete the T4 survey. Project website accounts for participants will be deactivated after completion of all study activities or expiration of the 14-day T4 survey completion window (if the T4 survey is not completed).

2.j. Medical Record Release. If a participant indicates he has received HPV vaccine during the T3 or T4 survey, the end of the T3/T4 survey will contain a link to a medical record release form that can be completed online (see Appendix). The form will open in a new window from the project website and be managed using Research Electronic Data Capture (REDCap). REDCap is a software toolset and workflow methodology for electronic collection and management of clinical and research data, to collect and store data. REDCap provides a secure, web-based application that provides an intuitive data manipulation interface, custom reporting capabilities, audit trail functionality, real-time data monitoring/querying of participant records, and variations of data exporting/importing. REDCap is hosted by OSUWMC IT in the Ackerman Datacenter. Participants will have the option of whether or not to complete the MRR form; those who do not will still continue in the study. Completing this form will allow the study team to contact the appropriate healthcare providers to confirm HPV vaccination status.

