Following completion of a participant's T4 survey or expiration of the 14-day T4 survey completion window (if the T4 survey is not completed), we will confirm HPV vaccination status via medical records (for those who completed an MRR form). A copy of the signed MRR form along with a request letter from the study team will be presented to a medical facility (via fax, phone, or secure email). The request letter will inform the facility about the study and request information from the medical record about the participant's HPV vaccination history be sent to the study team (via fax, phone, or secure email). Non-responding medical facilities will be contacted again by project staff.

2.k. Online Data Collection and Storage. As mentioned above, data from the MRR will be captured and managed via REDCap. REDCap is hosted by OSUWMC IT in the Ackerman Datacenter, and all data collected via REDCap is secured behind the OSUWMC firewall.

All other online data (e.g., from surveys, etc.) will be collected via the project website and stored by The Center for Health Communications Research (CHCR) at the University of Michigan.⁶³ CHCR ensures that data collection and storage processes are undertaken with attention to human subjects protections, respect for proprietary data, and maintaining integrity of the source data. CHCR was responsible for data storage and protection during our previous pilot study as well.

To ensure that the data are protected, CHCR uses virtualized servers provided by the University of Michigan Information Technology Services group. The virtualized servers are housed at two

redundant datacenters. These datacenters provide protection from lengthy outages, 24/7 staffing, restricted physical access, and disaster recovery. Virtual servers are backed up automatically onto encrypted tape for recovery and security. The datacenters also reduce the use of physical resources such as electricity and air conditioning.

All servers and the back-end databases are password protected. The server runs the Red Hat Enterprise Linux operating system and security patches and updates are downloaded and installed regularly. Each server is also protected by firewalls to restrict network access to the server. Additional details are available at <http://services.it.umich.edu/miserver/>.

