sexual minority (reports ever having oral or anal sex with a male or being sexually attracted to males; or identifies as gay, bisexual, or queer); d) lives in the US; e) has not received any doses of HPV vaccine; and f) did not participate in the pilot study. We will require men to read English and able to provide informed consent (inferred by completing the screener survey and consent form). All men will provide informed consent to participate in the RCT. The project website will provide participants with detailed information about the study prior to consent. For the RCT, participants will also be asked to provide medical record release (MRR), allowing for confirmation of HPV vaccination status during the study. The MRR form will be accessed through the project website and be managed using Research Electronic Data Capture (REDCap). A completed MRR form will not be required for study continuation.

2.b. Protection Against Potential Risk(s). Every means will be taken to minimize the risk associated with participating in this project. The autonomy of participants will be protected by informing all participants of the purpose of the study and allowing them to opt out of participation without repercuSSION. Participants will be able to withdraw from the study at any time, and they will be able to refuse to answer any question. Participants will be provided with study contact information in case they have any questions or concerns or experience any negative outcomes.

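### Does a man who signs a record release, but whose record never comes back, have no defined vaccination status?

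*Combined protocol and SAP*

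**What the plan says.** The source of the vaccination outcome is set out in three places.

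- Section 2.n (Potential Challenges, outcome ascertainment): "HPV vaccination status will be confirmed by medical records if MRR is provided, otherwise self-reported data will be used".
- Section 2.j (Medical Record Release) offers the form to a limited group: "If a participant indicates he has received HPV vaccine during the T3 or T4 survey". Signing is voluntary: "Participants will have the option of whether or not to complete the MRR form; those who do not will still continue in the study". After the T4 survey or the close of its window, "we will confirm HPV vaccination status via medical records (for those who completed an MRR form"). For silent facilities the only provision is "Non-responding medical facilities will be contacted again by project staff".
- Protection of Human Subjects, section 2.a, gives the meaning and purpose of the abbreviation: "participants will also be asked to provide medical record release (MRR), allowing for confirmation of HPV vaccination status during the study".

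Section 2.m says that all analyses follow intent-to-treat and that Aim 1 is tested by logistic regression and reported as odds ratios. It adds no rule for coding the outcome. On power it says "We will have at least 80% power for all comparisons".

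**The concern.** The condition in 2.n is whether a release was given, not whether a record was obtained. Consider two men who both report a dose. One declines the form and counts as vaccinated on his own word. The other signs, his facility never answers, and on a strict reading neither branch of the rule gives him a status. Nor does the plan say in terms how to code a record showing fewer or more doses than the survey.

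This could matter because everyone offered the form has reported vaccination, so every man in the gap is a reported event. Coding such men not vaccinated would lower the observed rates and pull the arms together. Coding them missing would lose events and sample size. The exposed contrast is Out-U versus Out-I on initiation (Hypothesis 1b), which has no spare power. If signing differed by arm, an adverse coding could also bias the comparison.

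**Working it through.** **Inputs from section 2.m.** "We will randomize about 2100 men (700 per arm"), with 70% retention, gives 700 × 0.70 = 490 per arm. Alpha is 0.017 two-sided, so the critical value is 2.387. Projected initiation is 20% (control), 35% (Out-U) and 45% (Out-I); projected completion is 10%, 22% and 35%.

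**Assumed input.** Let l be the share of reported vaccinees who signed and whose record is not returned, equal in all arms. The documents give no signing or return rates. The range 10% to 20% corresponds, for example, to 50% signing with 20% or 40% of facilities silent.

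**Formula.** Power = Φ(|p2 − p1| / se − 2.387), with se = √[p1(1 − p1)/n1 + p2(1 − p2)/n2].

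**Step 1: the plan's own figure.** For Out-U versus Out-I initiation, se = √[(0.35 × 0.65 + 0.45 × 0.55)/490] = 0.03113, and 0.10/0.03113 = 3.212. Power = Φ(0.825) = 79.5% (79.2% with a pooled variance). The stated 80% is reproduced to within a point. The odds ratio is (0.45/0.55)/(0.35/0.65) = 1.52.

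**Step 2: three ways to code the men in question.**

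- *Self-report kept:* the rates are unchanged.
- *Not vaccinated:* p becomes p(1 − l), and n stays 490.
- *Missing:* p becomes p(1 − l)/(1 − pl), and n becomes 490(1 − pl).

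| Coding | l | Out-U | Out-I | Odds ratio | Power |
|---|---|---|---|---|---|
| Self-report kept | any | 35.0% | 45.0% | 1.52 | 79.5% |
| Missing | 10% | 32.6% | 42.4% | 1.52 | 76.5% |
| Missing | 20% | 30.1% | 39.6% | 1.52 | 72.8% |
| Not vaccinated | 10% | 31.5% | 40.5% | 1.48 | 71.3% |
| Not vaccinated | 20% | 28.0% | 36.0% | 1.45 | 62.1% |

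The odds ratio in the missing rows does not move, for an algebraic reason. The odds become p(1 − l)/(1 − p), and the factor (1 − l) cancels between arms. The planned effect measure is not attenuated; only precision is lost.

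**Step 3: the other contrasts.** At l = 20%, coded not vaccinated, Out-U versus Out-I completion has 93.6% power. Control versus Out-U has 98.6% for initiation and 98.5% for completion.

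**Step 4: unequal signing, illustrated.** Suppose true initiation is 45% in both arms, 40% sign in one and 60% in the other, and 20% of facilities are silent. Coding not vaccinated gives 0.45 × (1 − 0.20 × 0.4) = 41.4% and 0.45 × (1 − 0.20 × 0.6) = 39.6%, a false gap of 1.8 points. Keeping self-report gives no gap.

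**Step 5: which coding the text supports.** Under 2.j the form appears at the end of a survey in which the man has just reported vaccination, so his self-report is already on file. Sections 2.j and 2.n and the human-subjects section all describe the record as confirming vaccination status, which presupposes a status to confirm. Nothing in the plan makes a report void when confirmation fails to arrive. The first row of the table is therefore the natural reading.

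The same wording implies that a returned record prevails over the survey. For initiation it can only overturn a yes. For completion it can move the count either way, since the vaccination history is requested even when T4 is missed.

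**The case for a change.** The best argument on the other side is that the abbreviation plainly means the release, so 2.n attaches the fallback to the wrong event. Three analysts could code the same man three ways and each point to the text. Such a choice is better fixed before data by arm are seen. An unequal loss could also do more damage than Step 4 shows: if 10% of Out-U and 20% of Out-I reported vaccinees were coded not vaccinated, the rates would be 31.5% and 36.0%, with 18.5% power (pooled variance).

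The point about wording stands: the sentence is loose, and the dose-count rule for completion is unstated. The rest is weaker. The damaging figures need an adverse coding that the plan nowhere adopts, together with signing and reply rates that it does not give. The unequal case also needs a difference between arms that nothing in the documents suggests. The thin margin on Hypothesis 1b comes from the sample size and exists whatever this rule says.

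A table of release uptake by arm and a model using self-report for everyone would be welcome extras, but the plan is not deficient without them. Nor is self-report for all clearly better. With an assumed 5% over-reporting in every arm, Out-U versus Out-I initiation power is 73.6% under that approach, against 75.4% when records correct the reports of the 30% assumed to sign.

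**Conclusion.** No change to the plan is needed. The gap is real but narrow: a fallback worded in terms of the form when it evidently means the record. Analysts would fill it by keeping the self-report when no record arrives and by letting a returned record prevail. On that reading every Aim 1 figure is as planned, including 79.5% power and an odds ratio of 1.52 for Out-U versus Out-I initiation. The alternatives, 76.5% to 73% power if coded missing and 71% to 62% if coded not vaccinated, rest on an assumed 10% to 20% share of affected men and on codings the documents do not call for. The conclusion depends on reading confirmation in its ordinary sense, as a check on a status already reported.
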